#### **5.6** Definition of Visit Windows

All data is to be presented by nominal visit date as recorded on the eCRF. Visits are not to be reassigned from the recorded nominal visit to any other visit based on dates.

## 5.7 Changes from the Planned Statistical Analysis in Protocol

The following changes from the analyses planned in the Protocol have been made:

- The protocol mentions that no missing data is to be imputed. Imputations for certain missing data items have been allowed for though (refer to Section 5.4: Handling of Missing, Unused, and Spurious Data).
- The protocol mentions one generalized estimating equation (GEE) model to be fit for ABR. Due to the difference in treatment regimens between protocol amendments, this has been adjusted to model twice weekly fixed dose regimen and PK-tailored regimen separately from the every 5 and 7 day treatment regimens.

#### 5.8 Statistical Tests

The default significance level is to be 5%; confidence intervals are to be 95% and all tests are to be two-sided, unless otherwise specified in the description of the particular analyses.

P-values obtained from statistical inference tests are to be presented using four decimal places. P-values smaller than 0.0001, are to be presented as "<0.0001" and p-values

larger than 0.9999, but les than 1, are to be presented as ">0.9999". A p-value of exactly 1 is to be presented as "1.0000".

Unless otherwise specified the default summary statistics for quantitative variables are to be as follows:

- The number of subjects in each category (n).
- Mean
- Standard deviation (SD).
- First quartile (Q1).
- Median.
- Third quartile (Q3).
- Inter quartile range (IQR) calculated as Q3 Q1.
- Minimum.
- Maximum.
- The number of subjects (n) with missing or unavailable results for quantitative variables is to be presented as "Not reported" where applicable. A "Not reported" category is only to be presented should there be unavailable results. No distinction based on the reason for unavailable results are to be made in any presentations.

If the original data has N decimal places (as derived from the raw data) (i.e., decimal precision [N]) then the summary statistics are to contain the following decimal places (with a maximum of three decimals, unless data warrants the use of more decimals):

- Minimum and maximum: N.
- Mean, median, Q1, Q3 and IQR: N+1.
- Standard deviation: N+2.

For qualitative variables the number (n) and percentage (%) of subjects in each category are to be the default summary presentation. Unless otherwise specified, percentages are to be calculated relative to the total number of subjects in the relevant analysis set as described in the latest version of the Output Templates. In the event of unavailable assessments a "Not reported" category is to be presented. A "Not reported" category is only to be presented if applicable. The "Not reported" category is to be presented with a percentage so that the sum of the percentages of all categories, including the "Not reported" category, totals 100%. No distinction based on the reason for unavailable results are to be made in any presentations.

All values are to be rounded using the SAS® function ROUND. All computed percentages are to be presented using one decimal place.

#### 5.9 Common Calculations

For quantitative measurements, change from baseline is to be calculated as:

Change from Baseline at Visit  $X = Test\ Value\ at\ Visit\ X - Baseline\ Value$ 

#### 5.10 Multicenter Studies

This study is conducted by multiple investigators at multiple centers internationally.

Unless otherwise specified, all summaries are to be produced overall and is not to be summarized by center.

## 5.11 Examination of Subgroups

The following subgroups are to be used in analyses as indicated in the latest version of the Output Templates:

- Treatment regimen at any time in the study as obtained from the *Treatment Assignment* and *Change in Treatment Assignment* eCRF forms:
  - o Fixed dose prophylactic treatment regimen.
  - o PK-tailored prophylactic treatment regimen.
- Age groups [years] (per different regional standards), using age at informed consent as obtained from the *Demographics* eCRF form:
  - o United States (US) age groups [years]:
    - Age < 2.
    - Age  $\ge 2$  to < 12.
    - Age  $\geq 12$  to < 17.
    - Age  $\geq 17$ .
  - o European (EU) age groups [years]:
    - Age < 6.
    - Age  $\geq$  6 to <12.
    - Age  $\geq$  12 to <18.
    - Age  $\geq$  18.
- Target joints at Screening as obtained from the *Hemophilia A History/Blood Group/Family History/Target Joint Identification* eCRF form:
  - o Present.
  - Absent.

- Number of bleeds during the study as obtained from the *Bleeding Episodes* eCRF forms:
  - No bleeds during the study.
  - o At least one bleed during the study.
- Treatment regimen prior to entering the Continuation study as obtained from the *Hemophilia A Treatment History* eCRF form:
  - o Prophylactic regimen.
  - o On-demand treatment.

## 5.12 Multiple Comparisons/Multiplicity

Not applicable.

#### 6. STUDY SUBJECTS

## 6.1 Disposition of Subjects

All subjects with informed consent provided are to be accounted for in this study.

Each subject is to participate in the study until a total of at least 100 EDs to BAX 855 have been achieved (accumulated across all BAX 855 studies in which each subject participated in).

Depending on the subject's BAX 855 exposure history and treatment regimen given, the planned duration of subject participation to reach the 100 EDs vary from approximately three to 12 months.

The following information is to be obtained from the eCRF:

- Informed consent (*Informed Consent* eCRF panels).
- Protocol version the subject enrolls onto the study (*Protocol Version* eCRF panels).
- Inclusion and exclusion criteria met and/or not met (*Inclusion/Exclusion Criteria* eCRF panels).
- Visit dates (*Date of Visit* eCRF panels).
- Other studies in the BAX 855 program the subject participated in (*Demographics* eCRF panels).
- Study completion (*Completion/Termination* eCRF panels):
- AE term and number (*Adverse Event* eCRF panels).
- Transfer to surgery study (if applicable; *Transfer to Surgery Study* eCRF panels).

- Return from surgery study (if applicable; *Return from Surgery Study* eCRF panels).
- Treatment regimen including date of treatment regimen start (*Treatment Regimen* and *Change in Treatment Regimen* eCRF panels).
- BAX 855 administration (*Study Infusions* eCRF panels).

The following derivations based on eCRF reported results are to be performed:

- A subject is considered to be enrolled if date of informed consent is present.
- A subject is to be assigned as dosed with a particular treatment regimen if the subject received any BAX 855 infusion when assigned to the particular regimen.
   Treatment regimen assignments are described in Section 5.11: Examination of Subgroups.
- A subject is considered to be completed if the reason for termination indicates the subject completed the study. Otherwise the subject is to be considered discontinued.

Planned presentation of tables on the disposition of subjects are to include a summary of disposition and analysis sets on the ENR set.

Planned presentation of listings on the disposition of subjects are to include information on previous BAX 855 studies participated in, disposition in current study, information on informed consent and eligibility, visit dates and analysis sets on the ENR set. Further listings are to include information on transfer and return from surgery study for subjects that did transfer to the surgery study.

## 6.2 Demographic and Baseline Characteristics

The following information is to be reported in the eCRF for demographic and baseline characteristics:

- Demographics (*Demographics* eCRF panels).
- Height and weight at Screening (Vital Signs eCRF panels).
- Information on hemophilia A history, blood group, family history and target joint identification at Screening (*Hemophilia A History/Blood Group/Family History/Target Joint Identification* eCRF panel).
- Estimated total number of documented previous FVIII EDs and average ABR based on previous three to six months (*Hemophilia A Treatment History* eCRF panel).

Should height not be recorded in the current study, height will be obtained from the Screening results of the predecessor study.

The following information is to be obtained from the Medical team based on medical histories reported in the *Medical History* eCRF panels:

- Whether a specific medical history can be considered as hemophilia arthropathy.
- Categorization of gene mutation for use in summaries.

The following information is to be obtained from the central laboratory:

• Hepatitis C virus antibody and HIV results at Screening.

The following derivations based on eCRF reported results are to be performed:

- Race is to be presented as 'Multiple' in summaries if more than one race is selected on the eCRF.
- Body mass index (BMI) is to be derived as:

$$BMI(kg/m^2) = Weight(kg) / \left[ \frac{Height(cm)}{100} \right]^2$$

- The number of target joints at Screening are to be counted from the eCRF.
- The number of target joints at Screening are to be counted from the eCRF.
- Average ABR based on previous three to six months are to be categorized as:
  - 0 < 1.
  - $\circ$  1 to <3.
  - $\circ$  3 to <5.
  - $\circ$  5 to <7.
  - $\circ$  7 to <10.
  - o 10 to <20.
  - $\circ$  20 to <30.
  - $\circ$  30 to <40.
  - o 40 to <50.
  - $\circ$  50 to <60.
  - 0 > 60.
- The presence of hemophilia arthropathy is to be determined as present if any medical history is present that can be considered as hemophilia arthropathy, otherwise is to be determined as absent.

Planned presentations of tables on demographic and baseline characteristics are to include baseline demographics and disease characteristics for the SAS, FAS and PPAS.

Subgroup analyses on demographic and baseline characteristics are to be performed by age, presence or absence of target joints at screening, initial treatment regimen in this study, and treatment regimen prior to entering the Continuation study.

Planned presentation of listings on demographic and baseline characteristics are to include baseline demographics and hemophilia A history, blood group and target joint specification at Screening for the SAS.

## 6.3 Medical History

Information on medical history is to be obtained from the eCRF (*Medical History* eCRF panels).

Medical histories are to be listed and summarized for the SAS. Medical history summaries are to be presented by age category.

## 6.4 Hemophilia A Treatment History

Information on hemophilia A treatment history is to be obtained from the eCRF (*Hemophilia A Treatment History* eCRF panel).

Hemophilia A treatment history is to be listed for the SAS. No summaries are to be presented for hemophilia A treatment history.

## 6.5 Prior PEGylated Medication History

Information on prior PEGylated medication is to be obtained from the eCRF (*Prior Pegylated Medication History* eCRF panel).

PEGylated medications are to be coded using the World Health Organization – Drug Dictionary Extended Version (WHO-DDE) as documented in the Data Management documentation at the time of performing the analysis.

Prior PEGylated medications are to be listed for the SAS. No summaries are to be presented for prior PEGylated medications.

## 6.6 Prior and Concomitant Medications and Non-drug Therapies

Information on prior and concomitant medications and non-drug therapies is to be obtained from the eCRF (*Concomitant Medications/Non-drug Therapies* eCRF panels). Information on AEs and medical histories for which the medication or non-drug therapy has been given, is to be obtained from the eCRF (*Adverse Event* and *Medical History* eCRF panels).

Medications are to be coded using the WHO-DDE as documented in the Data Management documentation at the time of performing the analysis.

The following derivations based on eCRF reported results are to be performed:

- Assignment to Prior or Concomitant:
  - A medication or non-drug therapy is to be assigned as 'Prior' if the medication or non-drug therapy stopped prior to first BAX 855 administration in the current study.
  - A medication or non-drug therapy is to be assigned as 'Concomitant' if the medication or non-drug therapy:
    - Started after first BAX 855 administration in the current study; or
    - Started before the first BAX 855 administration in the current study and ended after first BAX 855 administration in the current study or is still ongoing.
  - o A medication or non-drug therapy is to be assigned as 'Unknown' if missing dates do not allow for assignments based on above rules.
- Based on the reason for medication or therapy, the actual AE or medical history term is to be obtained linking the information from the particular eCRF panels.

Medications and non-drug therapies are to be listed for the SAS. No summaries are to be presented on medications or non-drug therapies.

## 6.7 Extent of Exposure

The following information is to be obtained from the eCRF:

- Information on study infusions (*Study Infusions* eCRF panels).
- Treatment regimen, including planned dose (*Treatment Assignment* and *Change of Treatment Assignment* eCRF panels).
- Body weight (*Vital Signs* eCRF panels).

The following derivations based on eCRF reported results are to be performed:

- Body weight-adjusted dose (IU/kg) is to be derived as the total units infused (IU) divided by the last available body weight (kg) prior to the infusion. Refer to Section 5.4: Handling of Missing, Unused, and Spurious Data for imputation schemes to be implemented.
- Total number of infusions in this study are determined as the count of the number of infusions, regardless of date and time, the subject had. Number of infusions are to be determined overall and by reason for infusion as well as by the treatment regimen assigned to at the time of receiving the treatment.
- The number of EDs are determined as the number of unique calendar days on which a subject received any or part of any infusion. Multiple infusions on the same day are still to be considered one ED. EDs are to be determined overall as well as for each reason an infusion is given. The number of EDs will be determined for this study and across all previous BAX 855 studies the subject participated in. EDs in this study will be derived as the number of infusions on unique calendar days in this study, while EDs from previous BAX 855 studies will be obtained as reported in the eCRF. The total EDs across all BAX 855 studies will be determined as the sum of EDs in current study and EDs in previous studies.
- The observation period for efficacy (OPE) in days in the study for subjects who never transferred to the surgery study is to be determined as:

$$OPE(Days) = (Stop\ Date - Start\ Date) + 1$$
 where "Start Date" refer to the first BAX 855 infusion in the current study and "Stop Date" to the last BAX 855 infusion in the current study. For subjects on the PK-guided regimen, first BAX 855 infusion will be the first prophylactic infusion.

• The OPE in days for subjects that did transfer to the surgery study is to be determined as:

$$OPE(Days)$$

$$= (Date\ of\ Transfer\ to\ Surgery\ Study - Start\ Date) + (Stop\ Date - Return\ Date\ to\ Current\ Study) + 1$$
where "Start\ Date" and "Stop\ Date" are\ defined\ as\ above.

• The OPE in weeks is to be determined from the OPE in days as:

$$OPE(Weeks) = \frac{OPE(Days)}{365.2425} \times 52$$

• The OPE in months is to be determined from the OPE in days as:

$$OPE(Months) = \frac{OPE(Days)}{365.2425} \times 12$$

• The OPE in years is to be determined from the OPE in days as:

$$OPE(Years) = \frac{OPE(Days)}{365.2425}$$

- All OPE calculations to be performed overall and per treatment regimen.
- The average number of infusions per time period (weeks, months, years) is to be determined as the total number of infusions during the observation period divided by the duration for the particular time period (weeks, months, years).
- Total dose (IU/kg or IU as applicable) is to be determined as the sum of all doses, overall and by reasons for infusion, during the observation period in the current study.
- The average dose per time period (weeks, months, years) is to be determined as the total dose (IU/kg or IU as applicable) the subject received during the observation period in the current study, divided by the duration for the particular time period (weeks, months, years).
- Average dose per bleed is determined as the sum of all doses (IU/kg or IU as applicable) given to treat bleeding episodes divided by the number of bleeds observed for the particular subject in the current study.

Extent of exposure is to be summarized using descriptive statistics for the SAS, and PPAS and listed for the SAS. Summaries are to be presented by age category and treatment regimen at time of dose.

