8.7.4 Treatment for Surgery or Dental Procedures

Subjects enrolled in this continuation study who require elective major or minor surgical or dental procedures or minor emergency surgical or dental procedures may be eligible to enroll in the BAX 855 surgery study (Study 261204), which is evaluating efficacy and safety of BAX 855 for perioperative management, if the study is open for enrollment. Exemptions may be granted for minor interventions in case the surgery study is not in place at the study site and the intervention can be managed by one prophylactic infusion and an additional infusion to maintain hemostasis. However, to ensure an adequate dose, at least an individual IR must be available which can also be based on FVIII activity levels determined at the local laboratory with back-up samples drawn for determination at the central laboratory. Any required major emergency surgery will result in withdrawal of the subject.

Upon completion of the surgery study, subjects may be eligible to return to this continuation study when they are able to resume their continuation study-specific prophylaxis regimen and with the approval of the sponsor's medical director. Upon return to this study, these subjects will receive their previous continuation study treatment regimen.

Subjects from this continuation study who participate in the surgery study will continue to receive their study-specific BAX 855 treatment from the continuation study as follows:

- For subjects undergoing PK (required for major surgery) or IR (required for minor surgery) assessment in the surgery study:
 1. From signing the informed consent until the pre-surgical PK^{vi}/IR^{vii} assessment required for major surgery.
 2. From completion of the pre-surgical PK/IR assessment until the loading dose prior to surgery.
- For subjects not undergoing PK/IR assessment in the surgery study:
 1. From signing the informed consent until the loading dose prior to surgery.

During the period from screening up to the loading dose prior to the surgery in which subjects receive BAX 855 from the continuation study, subjects will maintain their e-diaries for the continuation study, and the investigator of the continuation study will be responsible for the subject's safety and treatment. Any data collected during the above-listed periods will be recorded as part of this continuation study.

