During the pre-surgery PK assessment and during the period starting with the initial loading dose until the end of the surgery study, subjects will receive BAX 855 from the surgery study. Any data collected during these periods will be recorded as part of the surgery study.

EDs will be counted in the subjects' primary study, ie BAX 855 EDs accumulated as part of the surgery study will also be factored into the total number of EDs in the continuation study.

For subjects transitioning back from the surgery study to this study, the investigator will determine whether the subject continues to meet the eligibility criteria using end of study data from the surgery study.

8.7.5 . Investigational Product Accountability

The investigator will ensure that the IP is stored as specified in the protocol and that the storage area is secured, with access limited to authorized study personnel. The investigator will maintain records that the IP was received, including the date received, drug identity code, date of manufacture or expiration date, amount received and

vi Subjects undergoing major surgeries who have undergone a PK determination in the current study do not require a pre-surgical PK assessment.

vii Subjects undergoing minor surgeries but do not have an IR performed within 3 months of surgery have to perform an IR.

disposition. IP must be dispensed only at the study site or other suitable location (eg, infusion center, home, as applicable per study design). Records will be maintained that includes the subject identification code (SIC), dispensation date, and amount dispensed. All remaining partially used and/or unused IP will be returned to the study site, which will then return it to the sponsor or sponsor's representative after study completion/termination, or destroyed with the permission of the sponsor in accordance with applicable laws and study site procedures. If IP is to be destroyed, the investigator will provide documentation in accordance with sponsor's specifications.

For further detail, please refer to the pharmacy and IP distribution manual for this study.

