- A bleed is considered to be a minor bleed if the severity is indicated as "Mild" or "Minor".
- A bleed is considered to be a weekday bleed if the bleed occurred on a Monday, Tuesday, Wednesday, Thursday or Friday.
- A bleed is considered to be a weekend bleed if the bleed occurred on a Saturday or Sunday.
- A bleed is considered to be a morning bleed if the bleed occurred between 04:00 and 11:59.
- A bleed is considered to be an afternoon bleed if the bleed occurred between 12:00 to 17:59.
- A bleed is considered to be a night bleed if the bleed occurred between 18:00 and 03:59.
- A bleed is considered to have occurred at an unknown time if the time of a bleed is not available.
- Time since last prophylactic infusion in hours is to be derived as:
  - $Time(h) = Date/Time\ of\ Bleed\ Start\ Date/Time\ of\ Infusion$  where the start date/time of infusion refers to the last prophylactic infusion received (other than to treat a bleed) prior to the start of the bleed. Time since last prophylactic dose is to be categorized as:
    - $\circ$  <24 hours.

```
24 - <48 hours.

48 - <72 hours.

72 - <96 hours.

>96 hours.
```

• Time since previous bleed are only to be determine if a subject had multiple bleeds and is to be derived as:

```
Time(months)
= (Date/Time \ of \ Current \ Bleed
- Date/Time \ of \ Previous \ Bleed)/365.2425 \times 12
```

- A bleed is considered to be treated with BAX 855 if at least one infusion linked to the particular bleed is present in the *Study Infusion* eCRF panels. Infusions to "Maintain Hemostasis" are not to be summarized as part of treatment for bleeding episodes.
- The number of bleeds per subject overall and by location (target joint, non-target joint, joint and non-joint), causality (spontaneous/unknown and injury), severity (mild, moderate and severe) and timing (weekends, weekdays, morning, evening and afternoon) are to be determined as the count of unique bleeds in each category a subject had during the observation period.
- Annualized bleeding rate (ABR) is to be derived for each treatment regimen the subject had during the study as:

$$ABR = \frac{Number\ of\ unique\ bleeds}{OPE\ (years)\ for\ treatment\ regimen}$$

The ABR is to be analyzed using a generalized linear model fitting a negative binomial distribution with logarithmic link function. Only subjects that have 100 or more EDs are to be included in the models, where total EDs are derived as in Section 6.7: Extent of Exposure.

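### SAP 6.7 has no term for exposure days accrued in the surgery study during a mid-study transfer, although the protocol counts them, so subjects can wrongly fail the 100-ED rules

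*SAP*

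**What the plan says.** **Protocol.** Section 8.7.4 allows a mid-study surgery episode: "Upon completion of the surgery study, subjects may be eligible to return to this continuation study". While the subject receives product from the surgery study (the pre-surgery PK assessment, then from the loading dose to the end of that study), "Any data collected during these periods will be recorded as part of the surgery study". The EDs are nevertheless credited to the continuation study: "BAX 855 EDs accumulated as part of the surgery study will also be factored into the total number of EDs in the continuation study".

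**SAP, the count.** Section 6.7 gives two components and their sources. For the first, "EDs in this study will be derived as the number of infusions on unique calendar days in this study". For the second, "EDs from previous BAX 855 studies will be obtained as reported in the eCRF". The total is then fixed: "The total EDs across all BAX 855 studies will be determined as the sum of EDs in current study and EDs in previous studies".

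**SAP, where the count is used.** Section 7.1 applies it to the ABR models, including the co-primary spontaneous rate: "Only subjects that have 100 or more EDs are to be included in the models". That sentence refers back to 6.7 for the derivation. Section 8.3 restricts the inhibitor proportion to two groups: subjects who developed an inhibitor during the study, with no ED requirement, and inhibitor-free subjects with at least 100 EDs over every BAX 855 study and a central-laboratory inhibitor test after the 100th. Section 4.4 lists failure to reach 100 EDs among the possible major deviations to be discussed for the per-protocol set.

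**The concern.** EDs accrued in 261204 after a subject has entered this study fit neither SAP component. Their infusions are not in this study's infusion records, because the protocol sends them to the surgery study. Nor was the surgery study a previous study when the subject enrolled here.

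The protocol keeps a subject in the study until at least 100 EDs have been reached on its own count, which includes surgery EDs. A subject stopped soon after that point can therefore have done all that the protocol asked and still be below 100 when the SAP's rule is programmed. At stake is who enters the two co-primary analyses, and whether the SAP's evaluable subjects are the ones the protocol's target of 200 was meant to count.

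**Working it through.** **The plan's own figure.** The plan states about 250 enrolled to give 200 evaluable subjects with at least 100 EDs, citing a guideline. There is no power calculation or dropout rate to reproduce; 1 − 200/250 = 20% is only what those two numbers imply. The check is therefore on the counting rule.

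**Step 1: the two counts.** Let P be EDs in studies before entry, C the infusion days recorded in this study, and S the EDs in 261204 between transfer and return.

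- Protocol 8.7.4 total = P + C + S
- SAP 6.7 total, read literally = P + C

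A subject is wrongly classified when P + C < 100 ≤ P + C + S. The documents give no surgery EDs per subject, so every split below is an assumption.

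| P | C | S | Protocol total | SAP total | Passes SAP cut? |
|---|---|---|---|---|---|
| 0 | 92 | 10 | 102 | 92 | No |
| 50 | 45 | 5 | 100 | 95 | No |
| 50 | 40 | 10 | 100 | 90 | No |
| 0 | 85 | 15 | 100 | 85 | No |
| 50 | 30 | 20 | 100 | 80 | No |

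In the first row the subject would need 100 − 92 = 8 further EDs in this study, about 8/2 = 4 weeks at twice-weekly dosing, to satisfy the SAP. A subject who stays on that long is not lost.

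**Step 2: date of the 100th ED.** If the surgery precedes the 100th ED, the literal rule reaches that ED S exposure days after the protocol's count does. An inhibitor test taken in between comes after the 100th ED on the protocol's count but before it on the SAP's. If it is the subject's last test, SAP 8.3 drops the subject even though P + C passes 100.

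**Step 3: is the omission intended?** SAP 5.7 lists the departures from the protocol's analysis, and this is not one of them. SAP 6.1 takes other BAX 855 studies from one eCRF panel and surgery transfer and return from separate panels, and lists them separately. The observation-period formula in SAP 6.7, a few lines after the ED rule, takes the surgery interval out explicitly. Mid-study surgery was thus provided for, but the ED sum was given no matching term. SAP 4.2 names Minor Surgery panels, but only to identify who was dosed; nothing links them to EDs in 261204.

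**Step 4: effect on the inhibitor proportion.** Only inhibitor-free subjects can leave the denominator. I used the exact Clopper-Pearson 95% interval, whose upper limit for 0 of n is 1 − 0.025^(1/n). The starting n is the planned 200; the numbers lost are assumed. The surgery study plans about 40 subjects (Protocol 6.1), so 200 − 40 = 160 is the extreme.

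| n | 0 inhibitors: upper limit | 1 inhibitor: estimate (upper limit) |
|---|---|---|
| 200 | 1.83% | 0.50% (2.75%) |
| 190 | 1.92% | 0.53% (2.90%) |
| 160 | 2.28% | 0.63% (3.43%) |

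**Step 5: effect on the ABR.** The same subjects would leave the ABR models. The documents give no bleed rates for surgery subjects, so neither the size nor the direction of the effect can be computed.

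**The case against.** The best defence is that the SAP sentence defines a total over the whole programme, that 261204 belongs to the programme, and that the SAP does not define what makes a study previous. By the final analysis, a surgery study completed before return could be called previous, and the eCRF field for earlier EDs, which we cannot see, may already hold those days. This reading is possible but strained, because the SAP handles previous studies and surgery transfer as separate items throughout. At most it makes the inclusion rule ambiguous, and that also needs correcting.

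A second objection is that only SAP 7.1 cites 6.7; SAP 8.3 states its own requirement over every BAX 855 study, which on its face takes in surgery EDs. But that is the quantity that 6.7 defines by formula, and a programmer would naturally reuse it.

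A third objection, on reach, stands. The affected subject must transfer, return, and finish below 100 without surgery EDs but at or above 100 with them. Those who entered from the surgery study as their predecessor study are already counted. Participation runs to at least 100 EDs and may be extended. The figure of about 40 covers the whole surgery study, which also takes BAX 855-naïve subjects, so it is far from an estimate.

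A reader might go further and infer that the rule hides inhibitor cases, or that it removes a group at special risk of inhibitors. The documents support neither. SAP 8.3 keeps every subject who develops an inhibitor during the study at any ED count, and nothing in either document says that surgery subjects have a higher inhibitor risk.

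**Conclusion.** The ED total in SAP 6.7 is wrong as written. Followed literally, it undercounts EDs relative to Protocol 8.7.4 for anyone with a mid-study surgery episode, and it can exclude subjects who met the protocol's 100-ED target.

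The link to the ABR models is direct. The link to the inhibitor proportion runs through the shared definition of the total and is one-sided: with at least one inhibitor the estimate can only rise, and with none it stays at zero while the upper limit rises. On the assumed losses this is modest, and even the loose ceiling of 40 keeps the zero-inhibitor upper limit at 2.28%. The documents do not show a material threat to either co-primary result. The case for correction is that an inclusion rule for both should match the protocol and leave no room for interpretation.

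This conclusion assumes that the eCRF field for previous-study EDs does not already capture 261204 EDs accrued during this study. If it does, the numbers are right and only the wording needs to change.

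**What to change.** In SAP 6.7, define total EDs as EDs in the current study, plus EDs in BAX 855 studies completed before entry, plus EDs in 261204 accrued between transfer and return, including the pre-surgery PK infusion that Protocol 8.7.4 assigns to that study. Name the 261204 infusion records as the source of the third term. Count each calendar day once across studies, since a subject receives product from both studies around the transfer. State that this total, and the date of the 100th ED derived from it, govern the 100-ED rules in SAP 4.4, 7.1 and 8.3. Leave the observation period and the bleed counts as they are; the surgery interval is already removed there.

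The cost is a few lines of SAP text and a data link to another study in the same development programme. No new data collection and no protocol change are needed. Reporting how many subjects change status under the corrected count would settle its practical importance.
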